4.5 PHARMACOKINETIC ANALYSES

The Stage 1 PK analysis will be reported in a dedicated report.

For all Stage 2 subjects, pre-dose plasma concentrations of total PTX-2 will be presented descriptively at each time point by treatment group, including arithmetic and geometric means, median, range, standard deviations, and coefficients of variation.

4.6 BIOMARKER ANALYSES

All biomarker data will be presented in a dedicated report.

4.7 SAFETY ANALYSES

The safety analysis population will be used for all safety analyses. Analyses will be performed for both stages separately, as well as for the OLE phases.

4.7.1 Exposure to Study Medication

Information on study drug administration will be summarized by duration, starting dose, and cumulative dose. In addition, treatment exposure will be summarized, including the percentage of the planned dose given at each cycle.

Withdrawals of subjects from study treatment will be reported as listings and summary tables.

4.7.2 Adverse Events

Coding of all adverse events will be done using the latest version of the Medical Dictionary for Regulatory Activities (MedDRA). As part of the safety data transfer to Roche, the adverse events will be re-coded in legacy coding domain after database lock. Consequently, no queries are planned to be raised for any discrepancies in MedDRA Preferred Terms (PTs). This might result in some event terms that are vague (for example - 'heart problems') to be coded to less accurate, more high level concepts (eg Cardiac disorder for the example given). All AEs and routine laboratory parameters will be assessed according to the National Cancer Institute Common Terminology Criteria for Adverse Event (NCI CTCAE) version 4.0 grading system.

For AEs, the most extreme intensity will be used for reporting. All AEs occurring during or after the first treatment will be described by summary tables divided by body system, NCI CTCAE grade, and relation to study treatment. In tables showing the overall incidence of AEs, subjects who experienced the same event on more than one occasion are counted only once in the calculation of the event frequency and the AE with the most extreme severity will be included.

For selected events of particular interest (Infusion Related Reaction[IRR]) more detailed analyses will be conducted. The analyses will depend on the specific question of interest for that particular AE. IRR will be presented by anti-drug antibody status. In addition, the IRR event frequency and severity will be included in the analysis. Treatment discontinuations due to IRR will be listed.

AE leading to treatment discontinuations and early study withdrawals will be summarized by treatment group and by reason. In addition, all serious AE will be summarized.

Deaths reported during the study treatment period and those reported during follow-up (i.e. follow-up is 4 week after the last visit cycle) after treatment completion or discontinuation will be summarized by treatment group.

4.7.3 Laboratory Data

Laboratory values will be listed for subjects individually, with flagging of values outside the normal range. Shift tables will be used to present the number and percentage of subjects with changes in grade based on the NCI CTCAE version 4.0 grading system.

The frequency and percentage of positive, negative and untested serological laboratory parameters will be reported by cycle and treatment group.

4.7.4 Vital Signs

Vital signs (absolute and change from baseline) will be summarized according to treatment group over time without any replacement for missing data.

Electrocardiogram and physical exam abnormalities will be listed.

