Acute reactions in the monkey chronic toxicology study (1368-011) were first observed at the 200 mg/kg dose level on day 15, with continued occurrence on Days 15, 22, and 29. Most reactions resolved within ten minutes with therapeutic diphenhydramine, but deaths of two monkeys, one at 50 and one at 100 mg/kg, resulted in termination of the study.

These findings were unexpected because no acute infusion reactions, dose limiting toxicities, or deaths occurred in two prior GLP studies of 14 consecutive daily doses of PRM-151 in rats and monkeys, and because PRM-151 has already been administered safely to humans (as a single dose to 18 healthy volunteers and 3 subjects with idiopathic pulmonary fibrosis (IPF) and for multiple doses on days 1, 3, 5, 8 and 15 to 15 subjects with idiopathic pulmonary fibrosis). In studies 1368-010 and 1368-011, PRM-151 manufactured at CMC Biologics at the 2500 L scale and formulated at the testing site was administered to rats and monkeys on days 1, 3, 5, 8 and weekly thereafter. In prior GLP toxicology studies, PRM-151 DS manufactured at Catalent Biosciences at the 200 L scale with no additional formulation was administered to rats and monkeys on days 1-14. Both prior clinical studies utilized GMP drug product manufactured at Catalent Biosciences at the 200 L scale. To determine if the unexpected findings in studies 1368-010 and 1368-011 were due to differences in drug product or to differences in dosing schedule, and to explore mitigation of acute reactions by slower infusion rates, study 1368-012 was conducted.

Study 1368-012 in rats, assessed the frequency and severity of acute infusion reactions to both formulations of PRM-151 on both daily and weekly dosing schedules, and investigated the benefit of slower infusion rates in mitigation of acute toxicity. Animals in all arms received 200 mg/kg of PRM-151. Severe acute infusion reactions and deaths identical to the events in study 1368-010 occurred only on the intermittent bolus schedules and with all forms of PRM-151, indicating that the unexpected acute infusion reactions and deaths observed in studies 1368-010 and 1368-011 were due to intermittent dosing rather than product differences. Prolonging the rate of infusion to 60 minutes significantly reduced the frequency and severity of infusion

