### 1.3. Clinical Experience

PRM-151 has been evaluated in humans by intravenous administration in a Phase 1, single-ascending dose study in healthy subjects and subjects with idiopathic pulmonary fibrosis (IPF; PRM151A-11EU) and in a Phase 1, Multiple Ascending Dose Study in subjects with IPF (PRM151F-12GL) and in Stage 1 of PRM-151G-101, PRM-151 has also been evaluated in humans as a sub-conjunctival injection in a randomized, double-masked, placebo-controlled study of PRM-151 in the Prevention of Postoperative Scarring in Glaucoma Subjects Following Primary Trabeculectomy (PRM151B-21GL). The relevance to humans of acute infusion reactions observed in ongoing non-clinical toxicology studies is unknown; the reactions occurred at doses significantly higher than the dose intended in this study, and in vivo studies of recombinant human proteins in conventional animals are not particularly useful to assess the immunogenicity and risk of hypersensitivity reactions in humans since they are foreign to the animals. In Stage 1 of PRM-151G-101, two subjects each experienced a single, non-serious, Grade 2 hypersensitivity event, related to PRM-151. Both events were managed with medication. One subject developed the infusion reaction on Day 58 and continued to be treated with PRM-151. The other subject developed the infusion reaction on day 225 during the extension study. The hypersensitivity reactions to date have occurred as isolated events and have been manageable (refer to Investigator's Brochure for details).

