**Stage 1:**

Cohort 1: Approximately 12 subjects with intermediate -1, intermediate -2, or high risk MF who have received no treatment for MF in at least two weeks will be enrolled and assigned to treatment with single agent PRM-151 at a dose of 10 mg/kg IV on Days 1, 3, 5, 8, 15, and 22 of Cycle 1 and Days 1, 8, 15 and 22 of each subsequent 28 day cycle for six cycles, OR single agent PRM-151 at a dose of 10 mg/kg administered IV on Days 1, 3, and 5 of Cycle 1 and Day 1 of each subsequent 28 day cycle for six cycles. Subjects responding to therapy may continue receiving it as long as there is a benefit.

Cohort 2: Approximately 12 subjects with intermediate -1, intermediate -2, or high risk MF on a stable dose of ruxolitinib for at least 12 weeks, with no improvement in spleen during the last four weeks will be enrolled. Subjects will be assigned to receive PRM-151 in combination with ruxolitinib either at a dose of 10 mg/kg administered IV on Days 1, 3, 5, 8, 15, and 22 of Cycle 1 and Days 1, 8, 15 and 22 of each subsequent 28 day cycle for six cycles, OR in combination with ruxolitinib at a dose of 10 mg/kg administered IV on Days 1, 3, 5 of Cycle 1 and Day 1 of each subsequent 28 day cycle for six cycles. Subjects responding to therapy may continue receiving it as long as there is a benefit.

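### SAP 4.7 states no infusion-based denominator for infusion-related reactions, although planned infusions differ between the Stage 1 schedules (26 versus 8) and are open-ended in the extensions

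*SAP*

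**What the plan says.** For its tables of overall adverse event incidence, SAP 4.7.2 sets a once-per-subject rule: "subjects who experienced the same event on more than one occasion are counted only once in the calculation of the event frequency". Its next paragraph treats IRR apart: "For selected events of particular interest (Infusion Related Reaction[IRR]) more detailed analyses will be conducted". It promises a breakdown by anti-drug antibody status and a listing of discontinuations due to IRR, and adds: "In addition, the IRR event frequency and severity will be included in the analysis". It does not say whether that frequency is per subject, per infusion or per unit of time. The method is left open: "The analyses will depend on the specific question of interest for that particular AE".

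SAP 4.7.1 summarises exposure by duration, starting dose, cumulative dose and percentage of planned dose per cycle. Protocol 10.6.3.3, in the Stage 2 statistical section, also lists the number of injections received. SAP 4.7.1 does not.

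On dosing, the protocol's Appendix K sets out six cycles in Stage 1 and gives the weekly schedule as "Days 1, 3, 5, 8, 15, and 22 of Cycle 1 and Days 1, 8, 15 and 22 of each subsequent 28 day cycle". The other Stage 1 schedule has three infusions in Cycle 1 and one per cycle after that. Appendix L continues both schedules in the Stage 1 extension with no fixed end and lets subjects switch. Appendix J leaves the Stage 2 extension open-ended too. SAP 4.8 groups extension tables by the dose originally received, and overall.

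**The concern.** An IRR can arise at each infusion, so a subject given more infusions has more chances to be counted. Where groups differ in infusions by design, the share of subjects ever affected combines the risk per infusion with the number of infusions. Equal risks can then look different, and different risks can look equal.

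The only meaning SAP 4.7.2 gives to event frequency is the once-per-subject count, so a programmer could reasonably apply it to IRR as well. With infusions missing from the exposure table, a reader of the report could not easily correct for this.

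Two sets of results are exposed. One is the Stage 1 schedule comparison: protocol 1.5 cites no apparent difference in efficacy or safety between schedules as a reason for the Stage 2 schedule. The other is the two extensions, where subjects may contribute one infusion or many. Late reactions do occur: protocol 1.3 reports one on Day 58 and then "The other subject developed the infusion reaction on day 225 during the extension study". All Stage 1 subjects were assigned 10 mg/kg, so extension tables grouped by original dose would not, as written, separate weekly from four-weekly infusions.

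**Working it through.** The documents state no IRR rate, so there is no figure of the plan's own to reproduce.

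**Planned infusions, from the dosing schedules**
- Stage 1 weekly (Appendix K): 6 + 5 × 4 = 26
- Stage 1 every four weeks (Appendix K): 3 + 5 × 1 = 8; ratio 26/8 = 3.25
- Stage 2 main stage, each of the three arms (protocol 6.3): 3 + 8 × 1 = 11
- Stage 1 extension (Appendix L): 4 per cycle weekly, 1 per cycle every four weeks

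**Model (assumption).** With a constant, independent risk p at each infusion, the chance that a subject has at least one IRR in n infusions is 1 − (1 − p)^n.

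**Equal risk per infusion, Stage 1**

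| p | Weekly, n = 26 | Every four weeks, n = 8 | Ratio |
|---|---|---|---|
| 0.1% | 2.6% | 0.8% | 3.2 |
| 0.5% | 12.2% | 3.9% | 3.1 |
| 1% | 23.0% | 7.7% | 3.0 |
| 2% | 40.9% | 14.9% | 2.7 |
| 5% | 73.6% | 33.7% | 2.2 |
| 10% | 93.5% | 57.0% | 1.6 |

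The ratio drops below 2.5 once p exceeds about 3.2%, and below 2 once p exceeds about 6.4%.

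**Which part of the range is plausible.** Protocol 5.1.1 gives 27 Stage 1 subjects; Appendix K planned about 24. Assume a near-even split between schedules and all planned infusions given. The total is then between 12 × 26 + 12 × 8 = 408 and 14 × 26 + 13 × 8 = 468. One to two reactions give p between 1/468 = 0.2% and 2/408 = 0.5%, where the ratio is 3.1 to 3.2. Two is generous, since the second reaction came in the extension, outside these infusions.

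**Masking**
- 1% per infusion weekly and 3% every four weeks: 23.0% versus 21.6% of subjects, a ratio of 1.06 for a threefold difference.
- 2.0% every four weeks gives 1 − 0.98^8 = 14.9%. Solving 1 − (1 − p)^26 = 14.9% gives p = 0.62% weekly. A 3.2-fold difference in risk shows as no difference.

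**Extension example.** Six cycles of the Stage 1 extension mean 24 infusions weekly and 6 every four weeks. At an equal 1% per infusion this gives 21.4% versus 5.9%, a ratio of 3.7.

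**Stage 2 main stage.** With 11 planned infusions in every arm, equal risks give a ratio of 1 by design. A true 3% versus 1% shows as a ratio of 2.7, so a real difference is not hidden.

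**With infusions as the denominator.** Under the same model, equal risks give 1.0 and a threefold difference gives 3.0, whatever the number of infusions.

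**The case against.** The best defence is that the once-per-subject rule is confined to overall adverse event tables, and that IRR is singled out for fuller analysis in the following paragraph. This stands. A reader might infer that the SAP summarises IRR only per subject, but the text does not say so. What it shows is a denominator left unstated.

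Second, the one randomised comparison is sound on this point. This also stands: only unequal dropout could make infusions differ between the Stage 2 main-stage arms.

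Third, the Stage 1 schedule comparison can bear little weight. Appendix K has the investigator choose the schedule by the subject's ability to attend, numbers are small, and protocol 1.3 reports two reactions, one of them in the extension. This limits any result to description, but the final report will still present these groups side by side.

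Fourth, the proportion of subjects ever affected is a legitimate quantity, and a rate per infusion has its own weakness: if a susceptible minority reacts, subjects who tolerate many infusions dilute it. This is a good reason to keep the per-subject figure and to show first IRR by infusion number, not to omit infusions.

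Fifth, exposure is summarised elsewhere in SAP 4.7.1. Duration and cumulative dose give a rough guide, but neither is an infusion count or is linked to IRR.

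A reader might also infer from protocol 1.2.3, which says the severe animal reactions "were due to intermittent dosing rather than product differences", that the every-four-week schedule is the riskier one. The documents do not support that. The animal contrast was daily against weekly dosing, both Stage 1 schedules are intermittent in that sense, and protocol 1.3 calls the human relevance unknown.

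**Conclusion.** The point holds as a gap in specification with a predictable effect. SAP 4.7 plans no infusion-based or exposure-adjusted IRR measure, and the one counting rule it states would make IRR incidence depend on infusions received in the Stage 1 schedule comparison and in both extensions.

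The size is roughly threefold between the Stage 1 schedules when the risk per infusion is equal and about 1% or less, and about 2.2-fold at 5%. It rests on an assumed constant, independent risk per infusion and on planned rather than actual infusions.

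The point does not extend to the Stage 2 main-stage dose comparison, and it says nothing about which schedule carries more risk. It is a worthwhile, inexpensive improvement to the safety report and does not threaten the trial's main conclusions.

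**What to change.** In SAP 4.7.1, add the number of infusions received to the exposure table for each stage, extension and group.

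In SAP 4.7.2, state the denominator of the IRR event frequency. Keep the per-subject incidence and add, for the Stage 1 schedules and for both extensions:
- IRRs per 100 infusions, with an interval that allows for repeated events within a subject;
- cumulative incidence of first IRR by infusion number, censored at the last infusion.

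Split the Stage 1 extension by schedule, assigning each infusion to the schedule in force when it was given, because switching is allowed. Label all of this descriptive.

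Separating loading from maintenance infusions, separating premedicated infusions after a first reaction, and giving other extension adverse events per subject-year would be useful but optional.

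The cost is one exposure row, a rate table and a cumulative-incidence display. Protocol 6.9 and 7.13.1.1 already place infusion dates and times and adverse events in the eCRF. Those sections are written for Stage 2, so equivalent capture in Stage 1 is assumed. The drawback is wide intervals, since events are few.

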#### 1.3.2 Multiple Ascending Dose Study

The results of multiple-ascending dose study indicate that doses of PRM-151 administered by intravenous infusion over 30 minutes at doses of 1.0 mg/kg, 5 mg/kg, and 10 mg/kg on days 1, 3, 5, 8 and 15 are safe and well-tolerated. The most common AEs in the PRM-151 treated subjects

were cough (n=7; 47%), productive cough (n=4; 27%) and dizziness (n=4; 27%), followed by fatigue (n=3; 20%) and headache (n=3; 20%). The incidences of these events were similar in the placebo group (cough, 33%, productive cough, 33%; dizziness, 17%, fatigue, 17% and headache, 17%). Treatment emergent events of cough, dysphonia and hypotension were numerically more frequent in test article-treated subjects than in placebo-treated subjects. They occurred in PRM-151 treated subjects with the following frequencies: cough 40% (n=6), dysphonia 13% (n=2), hypotension 13% (n=2). No placebo treated subjects reported a treatment emergent adverse event of dysphonia or hypotension, and the frequency of cough was 17% (n=1). Frequency of treatment emergent productive cough was 33% (n=2) in the placebo treated subjects and 27% (n=4) in PRM-151 treated subjects.

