## **8.2. Cycle 1, Day 1 (+/- 1 day)**

- FDG or FLT PET-CT (where feasible) or CT or MRI (within 2 weeks prior to C1D1)
- Update medical history
- Re-assess inclusion/exclusion criteria
- MPN-SAF
- EORTC QLQ-C30
- IWG-MRT DIPSS (risk assessment)
- Abbreviated physical exam with spleen measurement
- Recording of concomitant medications
- Monitoring of adverse events
- Vital signs (before, immediately after study drug infusion and 1 hour post infusion)
- Weight
- ECOG Performance Status
- Urine pregnancy test for women of child-bearing potential (local lab)
- Complete blood count (CBC) (central lab)
- Chemistry evaluations (central lab)
- Coagulation parameters (central lab)
- Blood sample for Infusion Related Reaction Cytokines and anti-pentraxin 2 antibodies (pre-dose)
- Blood samples for genetic analysis
- Review of transfusions
- Review of excluded medications
- Blood sample for pentraxin-2 levels (pre-dose)
- Blood sample for anti-pentraxin 2 antibodies (pre-dose)
- Unblinded Pharmacist (or designee) to access IRS to randomize subject to dosing cohort
- PRM-151 administration

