### **10.6.2. Safety Analysis**

Safety evaluations will be based on the incidence, intensity, and type of adverse events, and clinically significant changes in the subject's physical examination, vital signs and clinical laboratory results. Safety variables will be tabulated and presented for all subjects who receive any amount of study medication. Exposure to study drug and reasons for discontinuation of study treatment will be tabulated.

Adverse events will be coded using the Medical Dictionary for Regulatory Activities (MedDRA) adverse event coding system for purposes of summarization. All adverse events occurring on study will be listed in by-subject data listings. Treatment-emergent events (TEAEs) will be tabulated, where treatment-emergent is defined as any adverse event that occurs after administration of any amount of study drug, or any event that is present at baseline but worsens in intensity or is subsequently considered drug-related by the Investigator. By treatment tabulations will be performed by MedDRA system organ class (SOC) and preferred term (PT) for deaths if any, serious adverse events; all treatment-emergent adverse events; TEAEs leading to discontinuation of study therapy due to adverse event or toxicity and TEAEs resulting in study discontinuation. Events that are considered related to treatment (possibly or probably drug-related) will also be tabulated. Tabulation will also be provided that enumerates adverse events by maximum severity.

Laboratory evaluations will be summarized by time of collection and by treatment group. In addition, change from baseline to any post-dose values will be summarized for vital signs and clinical laboratory results.

The frequency of subjects with abnormal safety laboratory results will be tabulated by treatment. Shift tables for each cycle will be produced for selected laboratory parameters, to include at least hemoglobin, WBC count, neutrophils, lymphocytes, platelets, AST, ALT, bilirubin, LDH, creatinine, alkaline phosphatase and electrolytes. These tables will summarize by cycle and dose level the number of subjects with each baseline CTC grade and changes to the maximum CTC grade in the cycle.

Clinically significant laboratory abnormalities will be tabulated or presented in individual data listings, depending on their number.

Vital signs assessments will be summarized over time in a similar fashion to laboratory parameters, and any abnormal values will be tabulated.

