**APPENDIX A Schedule of Events**

	Screening < 28 days	Cycle 1 28 Day Cycle Length			Cycle 2, 3, 4, 5, 6, 7, 8, 9, 28 Day Cycle Length	Cycle 9, Day 29	End of Study 
		Day (+/- 1 day)			Day (+/- 3 days)	(+/- 3 days)	(+/- 3 days)
		1	3	5	1		
Informed Consent	x						
Demographics	x						
Past Medical History	x	x					
Inclusion/Exclusion	x	x					
Bone Marrow Biopsy 	x				x	x	
Physical Exam 	x	x			x	x	x
IWG-MRT Response Assessment					x	x	
Prior/Concomitant Medications	x	x	x	x	x	x	x
Transfusion history (previous 12 weeks and between screening visit)	x	x			x	x	x
Review of transfusion diaries	x	x			x	x	x
AE/SAE Assessment 	x	x	x	x	x	x	x
Vital Signs 	x	x	x	x	x	x	x
Height (cm)	x						
Weight (kg)	x	x			x		
ECOG Performance Score	x	x	x	x	x	x	x
Pregnancy test 	x	x			x		
Complete Blood Count 	x	x			x	x	x
Chemistry, BUN/creatinine 	x	x			x	x	x
Coagulation 	x	x			x	x	
12 lead ECG 	x						
PET-CT Scan or CT or MRI 		x			x	x	
Exploratory laboratory assessments 		x				x	
Special list of excluded medications	x	x			x	x	x
Anti-pentraxin 2 antibodies, pre-dose		x			x	x	
Pentraxin-2 , pre-dose		x			x	x	
MPN-SAF 	x	x			x	x	x
EORTC-QLQC30 	x	x			x	x	x
Access IRS 	x	x	x	x	x		
IWG-MRT DIPPS (risk assessment)	x	x				x	

PRM-151 Administration 		X	X	X	X		
Infusion Related Reaction Cytokines and anti-pentraxin 2 antibodies 		X					

- 1 Bone marrow biopsy at Screening must have been performed within 4 weeks prior to first infusion of PRM-151; subsequent bone marrow biopsies on Cycle 4, Day 1, Cycle 7, Day 1 and on Cycle 9, Day 29 performed +/- 3 days of scheduled visit
- 2 Abbreviated physical exam including spleen measurement by palpation at all time points
- 3 Pre-treatment adverse events, including serious adverse events will be collected from the time of informed consent and after the medical history has been obtained
- 4 Vital signs (including temperature, blood pressure, pulse rate, and respiratory rate) will be performed before and immediately after PRM-151 infusion ,and at the conclusion of the one hour observation period
- 5 Serum pregnancy test within 4 weeks prior to the first dose of the study drug (central lab) Urine pregnancy test at all subsequent time points (local lab)

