### STAGE 1 OPEN LABEL EXTENSION STUDY

STAGE 1 OPEN LABEL EXTENSION STUDY		
SCHEDULE OF ASSESSMENTS	Weekly Dosing Extension Cycles	Q4 Weekly Dosing Extension Cycles

	28 Day Cycle Length				28 Day Cycle Length
	Day (+/- 3 days)				Day (+/- 3 days)
	1	8	15	22	Day 1
Informed Consent	x				x
Prior/Con Meds	x	x	x	x	x
AE/SAE assessment (1)	x	x	x	x	x
Vital Signs (2)	x	x	x	x	x
Weight (kg)	x				x
ECOG Performance Score	x				x
Urine Pregnancy Test	x				x
Complete Blood Count (3)	x				x
Chemistry, BUN/creatinine (4)	x				x
Transfusion History over past 3 months or since last visit	x				x
Special list of excluded medications	x				x
Anti-pentraxin 2 antibodies, pre dose (5)	x				x
PRM-151 Administration	x	x	x	x	x
Response Assessments (6)	x				x

1. Pre-treatment adverse events, including serious adverse events will be collected from the time of informed consent and after the medical history has been obtained
2. Vital signs (including temperature, blood pressure, pulse rate, and respiratory rate) will be performed before infusions.
3. CBC includes red blood cell count (RBC), hemoglobin, hematocrit, white blood cell count with differential, absolute neutrophil count (ANC), and platelets. Results should be reviewed prior to PRM-151 infusion. CBC can be drawn up to 7 days prior to PRM-151 infusion.
4. Blood chemistry lab parameters include lactic dehydrogenase (LDH), serum alanine aminotransferase (ALT), serum aspartamine aminotransferase (AST), direct and indirect bilirubin, alkaline phosphatase, creatinine phosphokinase (CPK), uric acid, calcium, phosphorus, sodium, potassium, chloride, bicarbonate, BUN, creatinine, and glucose.

5. Blood sample for anti-pentraxin 2 antibodies should be drawn pre-dose every 12 weeks. If the subject experiences an infusion related reaction, a blood sample for anti-pentraxin 2 antibodies should be drawn prior to any additional PRM-151 infusions.
6. The following components of response assessment will begin on Cycle 10, Day 1 and continue on Day 1 of every third cycle thereafter: Abbreviated physical exam and spleen measurements, MPN-SAF, and Investigator Response Assessment based on IWG-MRT criteria. Bone marrow biopsies will be performed only to determine or confirm a change in response category as described above.

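### SAP 4.7.4 omits the protocol's table of abnormal vital signs and does not use the readings taken around each Stage 2 infusion

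*SAP*

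**What the plan says.** **Collection.** Footnote 4 of the Stage 2 schedule (Protocol Appendix A) says vital signs "will be performed before and immediately after PRM-151 infusion ,and at the conclusion of the one hour observation period". Protocol 8.2 gives the same three times for Cycle 1 Day 1, and footnote 3 of the Appendix J schedule gives them for the Stage 2 extension. The Stage 1 extension differs: its vital signs "will be performed before infusions" (Protocol Appendix L).

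**Protocol analysis.** Section 10.6.2, which covers Stage 2, states: "Vital signs assessments will be summarized over time in a similar fashion to laboratory parameters, and any abnormal values will be tabulated". It also states that "change from baseline to any post-dose values will be summarized for vital signs and clinical laboratory results".

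**SAP analysis.** Section 4.7.4 reads: "Vital signs (absolute and change from baseline) will be summarized according to treatment group over time without any replacement for missing data". The same section then provides for listing ECG and physical examination abnormalities, but does not name vital signs there. Section 4 sets the default statistics for continuous variables: count, mean, standard deviation, median, minimum and maximum.

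**The concern.** The three-point measurement follows the infusion and the hour after it. Protocol 7.13.1.1 lists both hypotension and hypertension among the signs of an infusion reaction, and Protocol 1.3 records two related Grade 2 hypersensitivity events in Stage 1. These readings are the part of the acute-safety record that does not depend on an investigator deciding to report something.

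The SAP's summary does not use that timing. If post-infusion and pre-infusion readings are pooled, or only the pre-infusion reading is used, the summary says little about the infusion. Even if a post-infusion reading is used, change from a baseline months earlier mixes any infusion effect with drift between visits. Without the table of abnormal values, no output counts how many subjects in each dose group had an abnormal reading. Such a count could bring out a difference in unreported changes across 0.3, 3 and 10 mg/kg.

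**Working it through.** The plan states no figure for this point, so the main check compares the texts.

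| Item | Protocol (Stage 2) | SAP 4.7.4 |
|---|---|---|
| Summary over time by group | Yes (10.6.2) | Yes, absolute values and change |
| Change from baseline to post-dose values | Yes (10.6.2) | Change from baseline; reading not specified |
| Abnormal values tabulated | Yes (10.6.2) | Not mentioned |
| Definition of baseline for vital signs | Not in 10.6.2 | Not in 4.7.4 |
| Same-day pre- to post-infusion change | Not promised | Not planned |

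Two details matter.

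- **Baseline.** The schedule takes vital signs at both Screening and Cycle 1 Day 1, so baseline has more than one candidate. SAP 4.8 defines an extension baseline, but 4.7.4 does not say when it applies.
- **Comparison within the SAP.** Section 4.7.3 flags laboratory values outside the normal range and gives shift tables. Section 4.7.4 lists ECG and physical examination abnormalities. Vital signs get neither treatment.

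**Illustration of what a mean can show.** Inputs from the documents:
- Subjects per arm: 84 / 3 = 28 (Protocol 10.1 and 10.2).
- Planned infusions per subject: 3 in Cycle 1 + 8 in Cycles 2 to 9 = 11 (Protocol 6.3).

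Assumed inputs, because the documents give none: share affected p = 5% to 20%; fall d = 20 to 40 mmHg; standard deviation 10 to 20 mmHg.

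1. All affected subjects fall at the same summarised reading: shift = p × d. Low: 0.05 × 20 = 1.0 mmHg. High: 0.20 × 40 = 8.0 mmHg.
2. Each affected subject falls at one of the 11 infusions, spread evenly: shift per visit = p × d / 11. Low: 1.0 / 11 = 0.09 mmHg. High: 8.0 / 11 = 0.73 mmHg.
3. Scale for comparison: 1.96 × SD / √28. SD 10 gives 3.7 mmHg; SD 20 gives 7.4 mmHg. The SAP plans no confidence interval here, so this is only a yardstick for sampling noise in an arm mean.
4. Chance that an arm has at least one affected subject: 1 − (1 − p)^28. At 5% this is 76%; at 20% it is 99.8%.
5. Expected number affected: 28 × 0.05 = 1.4 to 28 × 0.20 = 5.6.

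Scattered falls move a visit mean by far less than the yardstick. Falls concentrated at one reading may or may not show: 1.0 mmHg would not, and 8.0 mmHg would exceed even the wider yardstick. A count of subjects shows either pattern if the falls cross the chosen limits.

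**The case against.** The strongest reply is that acute falls in blood pressure are covered elsewhere. Suspected infusion reactions must be reported regardless of severity (Protocol 7.13.2.1.1). Clinically significant vital-sign abnormalities are adverse events (7.13.1.1). SAP 4.7.2 analyses infusion reactions by frequency, severity and antibody status, and SAP 4.9 puts all available safety data into listings and tabulations. This largely stands. What it leaves out is a change that the investigator neither suspected as a reaction nor judged clinically significant. The general sentence in 4.9 sets no limits and yields no count by dose.

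A reader might infer that the SAP reports only mean change, so that hypotension disappears. The documents do not support that. Absolute values, median, minimum and maximum are planned, and reported events are counted. A minimum can reveal one extreme value, though not how many subjects were affected, and only if post-infusion readings are the ones summarised.

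A reader might also take the 13% hypotension (2 treated subjects, none on placebo) in Protocol 1.3.2 as an infusion-related rate. It is an adverse-event rate with no stated timing, and Protocol 1.4 says that study had no acute infusion reactions and no increase in toxicity with dose. It is not used here. Nor is a zero-rate comparison arm, since every Stage 2 arm receives drug.

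Two further points stand in part. The protocol never promised a same-day change, so that element is an addition. And the omission is read from silence: SAP section 1 refers to a detailed Stage 2 SAP, Version 2.0, which is not among the documents and may contain the table. However, the present SAP is the one that sets out the final analysis for the study report.

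**Conclusion.** The point holds as a reporting gap. A table to which Protocol 10.6.2 commits is absent from SAP 4.7.4 with no reason given. The remaining summary has no defined baseline and no stated within-visit reading, and makes no use of the same-day pre-infusion value. The consequence is limited: vital-sign changes not reported as adverse events or infusion reactions would not be counted by dose group. How many there might be cannot be derived from the documents, and the dilution figures rest on assumed incidence, fall and standard deviation.

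No efficacy conclusion is affected, and the documents do not show that a safety signal would be missed. The same-day comparison applies only where post-infusion readings exist, which excludes the Stage 1 extension. This is a low-cost improvement to secondary safety output.

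**What to change.** In SAP 4.7.4, before the final database lock:

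- Restore the protocol's table: number and percent of subjects with abnormal vital-sign values, by dose group, with the reporting limits fixed in advance.
- Define baseline for vital signs in the main stage, and say whether the extension baseline of SAP 4.8 is used for the extension.
- Summarise the pre-dose, end-of-infusion and one-hour readings separately, and add the change from the same-day pre-dose reading to each later reading. Apply this wherever post-infusion readings were taken; for the Stage 1 extension, state that only pre-infusion readings exist.

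If the sponsor prefers not to restore the table, the departure from Protocol 10.6.2 should be recorded with its reason in the study report, as Protocol 10.3.1 requires for changed methods.

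The cost is one or two extra tables from data already collected. No new procedure is needed, and the limits serve only to sort values for reporting; they change nothing in how subjects are treated or infusions managed.
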